17.0 Data Management and Analysis

17.1 Describe the data analysis plan, including any statistical procedures. This section applies to both quantitative and qualitative analysis.

Response:

Analytic plan is to use factorial ANCOVA to compare between group differences in different measures of DD, executive function and fMRI-measured brain function for subjects randomly assigned to poverty/neutral conditions and EFT/ERT. Covariates will be used if significant differences between groups are observed in subject characteristics. We predict a main effect of neutral/poverty, such that those assigned to poverty will have higher DD than those assigned to neutral, and an interaction between poverty/neutral and EFT such that in the poverty condition, EFT will reduce the discounting to levels achieved by the wealth, ERT subjects. We also predict when participants who receive EFT under challenge of poverty that EFT will increase activation in brain regions associated with delay of gratification (LPFC and AC) and prospection (hippocampus) relative to those who receive EFT under similar challenges.

17.2 If applicable, provide a power analysis.

NOTE: This may not apply to certain types of studies, including chart/records reviews, survey studies, or observational studies. This question is asked to elicit whether the investigator has an adequate sample size to achieve the study objectives and justify a conclusion.

Response:

The sample size is based on our studies of EFT versus ERT on DD in overweight and obese subjects, which showed an average AUC of $0.54 + 0.28$, and our unpublished research that poverty simulations reduces DD by 34%. We estimate in the ERT condition, neutral simulations will lead to less discounting and higher AUC than poverty simulations (0.54 vs 0.36). We estimate in EFT conditions, that simulations of neutral are associated with a small improvement in discounting in comparison to poverty simulations (0.63 vs 0.54). These predictions suggest that DD in EFT/Poverty and ERT/Wealth will be equivalent. The effect size for this interaction is 0.35. Using the overall SD we observed of 0.28, alpha of .05 and power of 0.80, we can show the effect size for this interaction with 17 Ss/group, or 68 total, or 34 per site in the behavioral portion and in the imaging portion. To be conservative, we will study up to 100 subjects.

17.3 Describe any procedures that will be used for quality control of collected data.

Response:

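### The effect size of 0.35 given for the interaction matches the overall spread of the four cell means; on the plan's own means the interaction f is 0.08, so 68 subjects give about 10% power, not 80%.

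*Combined protocol and SAP*

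**What the plan says.** Section 4.1 randomises the behavioural arm in a 2 × 2 design, poverty/neutral by EFT/ERT. Section 17.1 plans a factorial ANCOVA. It predicts a main effect of poverty and an interaction such that "in the poverty condition, EFT will reduce the discounting to levels achieved by the wealth, ERT subjects".

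Section 17.2 gives the planning values on the AUC scale, where higher means less discounting. Under ERT, "neutral simulations will lead to less discounting and higher AUC than poverty simulations (0.54 vs 0.36". Under EFT, "simulations of neutral are associated with a small improvement in discounting in comparison to poverty simulations (0.63 vs 0.54". It then states "The effect size for this interaction is 0.35". Taking a standard deviation of 0.28, a 5% significance level and a target power of 80%, the section concludes: "we can show the effect size for this interaction with 17 Ss/group, or 68 total, or 34 per site". The same number is applied to the behavioural and the imaging portions, and the ceiling is then raised to 100 as a margin. The effect-size metric is not named and no covariate correlation is assumed.

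**The concern.** The planned poverty effect is 0.18 under ERT and 0.09 under EFT. An interaction is the difference between these, 0.09, which is about a third of one SD as a contrast across four cells. In a 2 × 2 design a contrast of that size is hard to detect, and 17 per cell is far too few. An effect size of 0.35 on the f scale would be a large interaction, so the figure does not fit the means beside it.

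This is the only sample-size justification in the protocol. If the 80% is wrong, a non-significant interaction could be taken as evidence against the hypothesis by readers who were told that the study was adequately powered to find it.

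**Working it through.** **Inputs, all from Section 17.2.** Means: ERT/neutral 0.54, ERT/poverty 0.36, EFT/neutral 0.63, EFT/poverty 0.54. SD 0.28, alpha 0.05, target power 0.80. Equal cells are implied by 17 per group. The 0.36 is not a slip: 0.54 reduced by the plan's 34% is 0.54 × 0.66 = 0.356.

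**Method.** Noncentral F for a balanced 2 × 2 between-subjects ANOVA, with noncentrality λ = N·f² and denominator df N − 4. With one numerator df this is the two-sided test.

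**Step 1: reproduce the stated N.** With f = 0.35 and one numerator df, power is 78.7% at N = 64 and 81.1% at N = 68. So 17 per group is the first equal-cell size above 80%, and the plan's number is recovered by treating 0.35 as the f of a 1-df test.

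**Step 2: find where 0.35 comes from.**
- Grand mean: (0.54 + 0.36 + 0.63 + 0.54)/4 = 0.5175.
- Deviations, in the order listed above: 0.0225, −0.1575, 0.1125, 0.0225.
- Root mean square: √(0.038475/4) = 0.0981.
- Divided by the SD: 0.0981/0.28 = 0.350.

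This is the f for all differences among the four cells, a 3-df quantity.

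**Step 3: split it into its parts.**
- EFT versus ERT: marginal means 0.585 and 0.45, difference 0.135, f = 0.0675/0.28 = 0.241.
- Neutral versus poverty: marginal means 0.585 and 0.45, difference 0.135, f = 0.241.
- Interaction: contrast 0.18 − 0.09 = 0.09, each cell deviating by 0.09/4 = 0.0225, f = 0.0225/0.28 = 0.080.
- Check: 0.0581 + 0.0581 + 0.0065 = 0.1227 = 0.350².

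The interaction supplies 0.0065/0.1227, about 5% of the total; the main effects supply the other 95%.

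**Step 4: power on the plan's own means.**

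| Test | f or d | N = 68 | N = 100 | N for 80% (equal cells) |
|---|---|---|---|---|
| Interaction, 1 df | f = 0.080 | 10.0% | 12.5% | 1,220 |
| Any difference among cells, 3 df | f = 0.350 | 64.5% | 83.3% | 96 |
| Each main effect, 1 df | f = 0.241 | 49.9% | 66.5% | 140 |
| EFT versus ERT within poverty (0.18) | d = 0.64 | 44% (17 per cell) | 61% (25 per cell) | not calculated |

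For 80% interaction power at N = 68 the contrast would have to be about 0.386 AUC, against 0.09 planned.

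**Step 5: does the interaction test the stated prediction?** The prediction is that EFT/poverty reaches the ERT/neutral level. With no interaction at all, EFT/poverty equals ERT/neutral whenever the gain from EFT equals the loss from poverty. The prediction can therefore hold with a zero interaction, so the interaction test does not decide it.

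**The case against.** - **Origin of 0.35.** The plan shows no derivation, so saying that it came from the overall spread is an inference. That is fair. The inference reproduces both the 0.35 and the 17 per group, and the error does not depend on it: 0.35 is not the interaction f under the stated means, whatever its source. The contrast divided by the SD does not give it either (0.09/0.28 = 0.32).
- **A planned contrast.** The strongest alternative is that the investigators meant a 1-df contrast weighted to the predicted pattern of cells. Such a contrast has f = 0.350 and 81% power at 68; EFT/neutral against ERT/poverty alone has f = 0.341 and 79%. But Section 17.1 specifies a factorial ANCOVA, Section 17.2 calls the effect an interaction, and neither names a pattern contrast. It would also mostly reflect main effects.
- **Covariate adjustment.** The plan is an ANCOVA, so power could be higher than calculated. At assumed covariate–outcome correlations of 0.5 to 0.9, interaction power at 68 is only 12% to 32%.
- **Larger enrolment.** Sections 5.1 and 29.3 allow up to 250 across sites. That covers both arms, and Section 4.1 crosses the two factors only in the behavioural arm. All 250 in the 2 × 2 would give 24%, an upper bound that the design does not reach; an even split (125) would give 14.5%.
- **Other predictions.** Section 17.1 also predicts a poverty main effect, so the study does not rest on the interaction alone. That is true, but this effect has 50% power at 68 and 66.5% at 100.

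The choice of primary contrast remains the investigators'.

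**Conclusion.** The concern holds. On the plan's own means, SD and alpha, the interaction has f = 0.080 and about 10% power at 68 subjects, not 80%. It has 12.5% at 100 and would need about 1,220 subjects (305 per cell) for 80%. If all planning assumptions are true, about nine in ten studies of 68 would report no significant interaction. Reading the calculation as a 3-df test does not restore the claim (64.5% at 68), and neither main effect reaches 80% at 68 or 100.

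These figures assume equal cells, a common SD of 0.28, a two-sided test at 0.05 and no covariate gain. This should be corrected before the power statement is relied on.

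**What to change.** In Section 17.2, replace 0.35 with f = 0.080 for the interaction, state its power (about 10% at 68, 12.5% at 100), and label the interaction exploratory.

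In Sections 17.1 and 17.2, name one primary test that carries the hypothesis and give its power at the planned N. Two candidates are EFT versus ERT within poverty (0.18 AUC; 44% at 17 per cell, 61% at 25) and the EFT main effect (0.135 AUC; 50% at 68, 66.5% at 100). If the investigators intended a pattern contrast, they should write down its weights and say that it mostly reflects main effects.

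Prespecify adjustment for session-1 discounting. The documents give no baseline–outcome correlation; assuming 0.5 to 0.8, EFT main-effect power at 68 is 62% to 90%, and within-poverty power at 25 per cell is 73% to 96%. Reaching 80% for the latter needs a correlation of about 0.6. First reconcile Section 10.1: the behavioural-arm text appears to place the episodic thinking task in the second session, while the fMRI-arm text refers to it in the behavioural arm's first visit. Session-1 discounting is a clean baseline only if it precedes that task.

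Report EFT/poverty minus ERT/neutral with a confidence interval, and do not infer equivalence from a non-significant difference.

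The cost is rewording of 17.1 and 17.2, with no extra subjects. The stated power becomes less favourable, and 80% at 100 subjects then depends on the assumed baseline correlation.

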18.0 Confidentiality

A. Confidentiality of Study Data

Describe the local procedures for maintenance of confidentiality of study data and any records that will be reviewed for data collection.

18.1 A. Where and how will all data and records be stored? Include information about: password protection, encryption, physical controls, authorization of access, and separation of identifiers and data, as applicable. Include physical (e.g. paper) and electronic files.

Response:

The i2b2 data will be protected by only accessing identifiable contact information remotely on IHI's "virtual machine", so the identifiable data never leaves their secure encrypted server. All use of identifiable data is done behind the firewall on IHI's secure system.

Potential participants who have filled out the prescreen survey will have their responses stored on a password protected server that only the research staff will have access too. Additionally, if there are paper copies of the prescreen survey responses they will be de-identified and stored in a locked filing cabinet in a locked room (252A Farber hall) which only research staff has access to.

Participants will be assigned a unique identification number to ensure the confidentiality of the data. A master list that links subject ID and participant's name will kept in a secure file that is password protected on a password protected computer. Only research staff will access to the master list. Paper files will be kept in locked lab offices at the Division of Behavioral Medicine Research Lab and electronic files will be kept on password protected computers in password protected/encrypted databases only accessible to members of the research staff. When the results of the study are presented and/or published, only group data will be provided; no individual participant will be identifiable.

18.2 A. How long will the data be stored?

Response:

Data will be retained for a period of at least three years. The master list linking the study ID with the participant name will be kept in a locked cabinet in G56 for three years after the completion of the study at which point it will be destroyed. De-identified data will be retained indefinitely.

18.3 A. Who will have access to the data?

Response:

Only the principal investigator and research staff associated with the study will have access to the data.

18.4 A. *Who is responsible for receipt or transmission of the data?*

Response:

The principal investigator takes primary responsibility for the data.

18.5 A. *How will the data be transported?*

Response:

Data will be transported in password protected/encrypted files via email. fMRI data will be uploaded from DENT to a DICOM server so that Researchers at Virginia Tech are able to analyze imaging results. All transferred data will be de-identified

B. Confidentiality of Study Specimens

*Describe the local procedures for maintenance of confidentiality of **study specimens**.*

- N/A: No specimens will be collected or analyzed in this research.
(Skip to Section 19.0)

18.6 B. *Where and how will all specimens be stored? Include information about: physical controls, authorization of access, and labeling of specimens, as applicable.*

Response:

All blood and urine samples will be analyzed during or immediately after the initial screening appointment and will not be saved (i.e., stored). Data will not be banked for future use.

18.7 B. *How long will the specimens be stored?*

Response:

N/A, specimens will not be stored.

18.8 B. *Who will have access to the specimens?*

Response:

Research staff conducting appointments will have access to the specimens during or immediately after the initial screening appointment. However, specimens will not be stored.

18.9 B. *Who is responsible for receipt or transmission of the specimens?*

Response:

N/A, there is no receipt or transmission of the specimens.

18.10 B. How will the specimens be transported?

Response:

N/A, the specimens will not be transported.

19.0 Provisions to Monitor the Data to Ensure the Safety of Subjects

- N/A: This study is not enrolling subjects, or is limited to records review procedures only. This section does not apply.

NOTE: Minimal risk studies may be required to monitor subject safety if the research procedures include procedures that present unique risks to subjects that require monitoring. Some examples include: exercising to exertion, or instruments that elicit suicidality or substance abuse behavior. In such cases, N/A is not an acceptable response.

19.1 Describe the plan to periodically evaluate the data collected regarding both harms and benefits to determine whether subjects remain safe.

Response:

Data will be reviewed weekly and secured in Division of Behavioral Medicine Research Lab. The Principal Investigator, [name], will be responsible for ensuring data integrity and safety monitoring for human subjects who are involved in the research along with the Data Safety Officer.

19.2 Describe what data are reviewed, including safety data, untoward events, and efficacy data.

Response:

Study questionnaires and measurements that are collected by study personnel will be reviewed and monitored.

19.3 Describe any safety endpoints.

Response:

This study poses no greater than minimal risk; therefore, there are no safety endpoints.

19.4 Describe how the safety information will be collected (e.g., with case report forms, at study visits, by telephone calls with participants).

Response:

Participants will be encouraged to contact study personnel if they experience any problems or difficulties, and if any adverse events (AE) are reported, the study personnel contacted will record the AE. AE will be recorded as soon as they are reported, and the PI and study coordinator will be made aware. The study coordinator will summarize the AE in a memo; the participant will be called and the summary will be read to them to ensure that the information is accurate. The

memo will then be submitted to the University at Buffalo IRB and the PI. If the PI, or the IRB decide that further action is warranted, the PI and study coordinator will then formulate and carry out a plan to respond to the AE. The study coordinator will write a memo summarizing such actions; this memo will then be forwarded to the IRB. Safety information will be collected and reported to both the UBIRB and the Safety Officer in the time frames outlined by the UBIRB.

19.5 Describe the frequency of safety data collection.

Response:

Data will be reviewed weekly and secured in G56 and G252A Farber Hall. A weekly review of these data will be conducted by the principal investigator and project coordinator during their staff meetings with study personnel.

19.6 Describe who will review the safety data.

Response:

Serious Events and Problems (SEP) will be monitored by the principal investigator and project coordinator as well as reported to both the IRB and the Safety Officer in the timeframes outlined by the IRB.

19.7 Describe the frequency or periodicity of review of cumulative safety data.

Response:

Cumulative data will be reviewed approximately six months to a year based on the requirements of the Grant and NIH committee.

19.8 Describe the statistical tests for analyzing the safety data to determine whether harm is occurring.

Response:

N/A, there are no discontinuing criteria.

19.9 Describe any conditions that trigger an immediate suspension of the research.

Response:

N/A, there are no discontinuing criteria.

20.0 Withdrawal of Subjects

N/A: This study is not enrolling subjects. This section does not apply.

*20.1 Describe **anticipated** circumstances under which subjects may be withdrawn from the research without their consent.*

Response:

Subjects who do not adhere to the protocol procedures and study instructions may be withdrawn from research analyses, as determined by the Principal Investigator and/or NIH Data Safety Committee. In addition to not adhering to study

instructions, possible reasons for removal include nonsystematic responding to questionnaires and HbA1c (blood sugar) levels that are not in the prediabetes range. If a participant is withdrawn from the study without their consent, they will be debriefed about the nature of the study and be compensated for the amount of time spent in the study. We may also stop an ongoing session, or end participation in the study because we have collected all the information we need.

20.2 Describe any procedures for orderly termination.

NOTE: Examples may include return of study drug, exit interview with clinician. Include whether additional follow up is recommended for safety reasons for physical or emotional health.

Response:

Participants will be debriefed about the nature of the study and the reason for their removal, if a safety concern. No additional follow-up is needed.

20.3 Describe procedures that will be followed when subjects withdraw from the research, including retention of already collected data, and partial withdrawal from procedures with continued data collection, as applicable.

Response:

Participants can withdraw from the research at any time. If participants withdraw, no further data will be collected, but any information that had been provided may be retained by the researcher and analyzed.

21.0 Risks to Subjects

21.1 List the reasonably foreseeable risks, discomforts, hazards, or inconveniences to the subjects related to their participation in the research. Consider physical, psychological, social, legal, and economic risks. Include a description of the probability, magnitude, duration, and reversibility of the risks.

NOTE: Breach of confidentiality is always a risk for identifiable subject data.

Response:

There may be some sensitivity associated from certain questions asked when filling out questionnaires or having body measurements taken and subjects might feel uncomfortable disclosing some personal information such as medical history. Subjects can refuse to answer any questions that they are not comfortable answering. Subjects will be free to withdraw from the study at any time, and their refusal to continue will not affect other medical care provided at any healthcare facility.

Participants may experience hunger due to refraining from eating before the session or possibly suffer a new allergic reaction to the PowerBar (i.e., an allergic reaction to a food to which he/she was not allergic in the past). Feelings of hunger will subside when the participant is able to eat after the session and the study food used is a common food thus researchers anticipate that participants will know if they should avoid eating them for

medical, religious, or preference reasons. In addition, only personnel certified in CPR, first aid, and AED will conduct study sessions and these individuals are trained to contact appropriate medical personnel in the event of an emergency.

Breach of confidentiality is another potential risk. The studies will occur in our facilities at the University at Buffalo and the Virginia Tech Carilion Research Institute. To protect confidentiality, we will use only ID numbers and keep all data in locked cabinets or in locked offices and password protected electronic files in password protected computers. Any data shared between sites will involve de-identified data only and files will be encrypted or password protected. These screening, monitoring, and confidentiality procedures have been in effect for more than 10 years and for more than 2,000 subjects across the various protocols employed by our group.

Participants may have a small bruised area on the finger from the pinprick site. The bruise should fade over time without treatment. If during the course of the study, a subject's blood glucose exceeds the range for prediabetes (Fasting Plasma Glucose (FPG) 100-125 mg/dl, or 2h glucose 140-199 mg/dl after Oral Glucose Tolerance Test (OGTT) or hemoglobin A1c (HbA1c) 5.7-6.4%), that subject will be directed to his or her physician or other medical care provider for further evaluation.

Participants may have their blood pressure measured. If during the course of the study, a subject's blood pressure reaches hypertensive crisis (180/110 mmHg), that subject will be directed to his or her physician or other medical care provider for further evaluation.

During the fMRI, movement or heating of metallic implants is a potential risk; subjects will thus be carefully screened to exclude individuals with metallic implants, fragments, or pacemakers. Some individuals may experience mild discomfort or anxiety in the scanner, and all subjects will be informed of this possibility prior to the study. In addition, throughout the scanning procedures, subjects will be able to communicate with the investigators via intercom, and any individual experiencing discomfort will be removed from the scanner immediately.

As noted, physical risk to subjects during fMRI recording is very low. Nevertheless, in addition to the measures to ensure the safety and comfort of subjects noted above, every effort will be made to provide information to subjects to minimize discomfort. There may be additional risks associated with scanning at 3 T compared to the conventional clinical scanners in the 1.5-2.0 T range. These include:

Effect of the static field. There is no conclusive evidence for irreversible or hazardous bioeffects to acute, short-term exposures of humans up to 2.0 T (Shellock et al., 1996). Studies have indicated some side-effects at 4.0 T, namely unusual sensations including nausea, vertigo, and metallic taste. However, there is no evidence that these effects are either irreversible or

harmful. If subjects experience unusual sensations, they will be withdrawn.

Effect of the gradient field. MRI operates by rapidly changing small additional fields, called gradients. This will induce small electrical currents in any conductor, and thus could theoretically induce mild peripheral nerve stimulation. However, this is not substantially different at higher magnetic fields as the gradients are separate from the main magnet. There is no evidence that the effect of the gradients is any different at 3 T than at 1.5 T. However, if subjects experience peripheral nerve stimulation such as tingling or twitching, they will be withdrawn.

Effect of the RF electromagnetic field. The higher magnetic field strength requires that higher RF frequency pulses be used to excite the protons in the subject's brain. The limits of RF energy that can be safely given to humans has been clearly defined by the FDA: a) The exposure to RF energy below the level of concern is an SAR of 0.4 W/kg or less over the body, and 8.0 W/kg or less spatial peak in any 1 g of tissue, and 3.2 W/kg or less averaged over the head; or b) The exposure to RF energy that is sufficient to produce a core temperature increase of 1 degree C and localized heating to no greater extent than 38 degrees C in the head, 39 degrees C in the trunk, and 40 degrees C in the extremities, except for patients with impaired systemic blood flow and/or perspiration. The scanner has a large monitor indicating the RF power level which can be limited to a specific maximum, and we will adhere to the recommendations.

There are no other risks anticipated. All personnel on the study will be CITI course certified and have completed the good research practices certification. All identifiable data will be password protected and only the research team will have access to that information. Subjects will be informed of the risks associated with the study.

21.2 Describe procedures performed to lessen the probability or magnitude of risks, including procedures being performed to monitor subjects for safety.

Response:

We have several provisions in place to ensure participants' privacy and safety is protected while the data is being collected. The lab facilities of the Division of Behavioral Medicine research laboratory consist of private interview rooms that will be used. Only the interviewer and participant will be present in the room during interviews. Data is recorded such that not even the person putting it in the file would ever be able to associate the data with the identity of the person providing it. Data and files that have been de-identified and encrypted will be shared between sites. Therefore, there is no reasonable risk of a breach of confidentiality. Only personnel certified in CPR, first aid, and AED will conduct study sessions and these individuals are trained to contact appropriate medical personnel in the case of a serious event. Should an emergency situation occur, access to further

medical care is available via a telephone located in the laboratory and the following emergency plan will be followed:

1. Have the subject immediately stop any activity and lay down.
2. Call for help! ON CAMPUS EMERGENCY [contact]) or POLICE (911).
3. If the subject is unconscious – assess breathing and heart rate. Initiate CPR and call on campus emergency services or police as necessary.
4. If the subject is conscious – continue to observe subject.

*21.3 If applicable, indicate **which procedures** may have risks to the subjects that are currently unforeseeable.*

Response:

N/A, subjects will be allowed to refuse to answer any questions they are not comfortable with.

21.4 If applicable, indicate which research procedures may have risks to an embryo or fetus should the subject be or become pregnant.

Response:

MRI scans are not recommended for pregnant individuals. We will offer urine pregnancy test for females at the beginning and throughout the study. We will notify females of positive pregnancy test results and discontinue them from the study.

21.5 If applicable, describe risks to others who are not subjects.

Response:

N/A, no foreseeable risks to others who are not subjects.

